7.2 ASSESSMENT OF ADVERSE EVENTS

AE SEVERITY

Investigators will grade the severity of all AEs using the Common Terminology Criteria for Adverse Events (CTCAE). If possible, investigators should report event terms that reflect a single, unifying diagnosis rather than individual signs or symptoms (e.g., “influenza” instead of “coughing, body aches, fever;” and “anemia” rather than “low hemoglobin”).

If an AE term is not listed in the CTCAE criteria, a corresponding grading is to be performed by the investigator based on his/her best medical judgment as follows:

- **Mild (Grade 1):** asymptomatic or mild symptoms; clinical or diagnostic observations only; intervention not indicated
- **Moderate (Grade 2):** minimal, local, or noninvasive intervention indicated; limited age-appropriate instrumental activities of daily living (ADL)
- **Severe (Grade 3):** medically significant but not immediately life-threatening; hospitalization or prolongation of hospitalization indicated; disabling; or limiting self-care ADL
- **Life-threatening (Grade 4):** life-threatening consequences; urgent intervention indicated
- **Fatal (Grade 5):** death related to an AE

AE CAUSALITY

Investigators are required to systematically assess the causal relationship between the AEs and SAEs and the treatment using the following definitions:

An event should be reported as related to the study treatment if it follows a reasonable temporal sequence to use of the investigational device and cannot be reasonably explained by the participant’s clinical state or other factors (e.g., disease under study, concurrent diseases, or concomitant medications); OR the AE follows a reasonable temporal sequence to use of the investigational device and is a known reaction to the investigational device.

An event should be reported as unrelated to study treatment if it does not follow a reasonable sequence from an investigational device, or it can be reasonably explained by the participant’s clinical state or other factors (e.g., disease under study, concurrent diseases, and concomitant medications).

7.3 SERIOUS ADVERSE EVENTS

An SAE is any AE that meets any of the following criteria:

- Results in death
- Is *life-threatening*
- Requires inpatient *hospitalization* or prolongation of existing hospitalization
- Results in persistent or significant *disability/incapacity*
- Is an *important medical event*

Sponsor Name: Woebot Health

Protocol Number: WB001-001

UNANTICIPATED ADVERSE DEVICE EFFECTS

A suspected unanticipated adverse device effect (UADE) is defined as an untoward and unintended response to a study treatment, which is not listed in the applicable product information, and meets at least one AE or SAE criterion, and is assessed as causally related to the study treatment. The Sponsor or designee will be responsible for carrying out required reporting to investigators, health authorities, and other entities as required by law.

DOCUMENTING AND REPORTING ADVERSE EVENTS AND SERIOUS ADVERSE EVENTS

Reporting of non-serious AEs and SAEs will begin at the time of first interaction with the app and will continue through EOT. Any new clinical condition or worsening of existing conditions between the time the informed consent form (ICF) is signed, and the first use of the study intervention will be recorded as AE/SAEs unrelated to the device.

AEs and SAEs may be reported spontaneously by participants, discovered as a result of general, non-leading verbal questioning by the study staff, or determined by assessments. As needed, qualified study staff will inform investigators to inquire about any new symptoms or worsening of symptoms during the telehealth visits at Weeks 4 and 8. In the interim, participants will be instructed to contact the investigator if new or worsening symptoms develop outside of key assessment visits. All incidences confirmed as AEs or SAEs will be monitored and recorded in the eCRF throughout the entire study.

The investigator must pursue and obtain adequate information about all incidences they deem as AEs and SAEs. At minimum this includes a description of the event, severity, device relatedness, start and stop times, duration, outcome, and any action (e.g., treatment/follow-up tests). The investigator must also assess whether the event meets the criteria for classification as an SAE.

It is the investigator's responsibility to review all documentation (e.g., hospital notes, laboratory reports, and diagnostic reports) related to an AE or SAE. Whenever possible, a single unifying diagnosis should be reported as the event term, and not the individual signs and symptoms.

Investigators are not obligated to actively seek AEs or SAEs after the participant's conclusion of study participation. However, if the investigator learns of any SAE, including death, at any time after a participant has been discharged from the study, and he/she considers the event to be reasonably related to the investigational device or study participation, the investigator must promptly notify the Sponsor.

REPORTING OF SERIOUS ADVERSE EVENTS

The investigator must immediately report SAEs to the Sponsor or designee (no later than 24 hours after becoming aware of the event) using the SAE report form.

The investigator is obliged to promptly respond to any request for follow-up information (e.g., additional information, event outcome, final evaluation, or other records if needed) and to any question from the Sponsor or designee. This timely reporting is necessary to ensure prompt assessment of the event by the Sponsor or designee and to allow them to meet strict regulatory timelines associated with expedited reporting obligations for SAEs.

Sponsor Name: Woebot Health

Protocol Number: WB001-001

The Sponsor has a legal responsibility to notify both the local regulatory authority and other regulatory agencies about the safety of a study intervention under clinical investigation. The Sponsor will comply with country-specific regulatory requirements relating to safety reporting to the regulatory authority, IRB, and investigators.

An investigator who receives an investigator safety report describing an SAE or other specific safety information (e.g., summary or listing of SAEs) from the Sponsor will review and then file it along with the Investigator's Brochure and will notify the IRB, if appropriate according to local requirements.

All serious and/or possibly related or related (to the device or study procedure) AEs will be reported to the DSMB and reviewed on an on-going basis throughout the participant enrollment and follow-up period as specified in the DSMB charter to ensure the safety of participants enrolled in this study. The DSMB may request additional information as needed. Based on safety data, the DSMB may recommend that the Sponsor modify or discontinue the study; however, all final decisions regarding study modifications rest with the Sponsor.

AE AND SAE FOLLOW-UP

During the study (and after the EOT visit), all AEs and SAEs should be followed proactively by the investigator or qualified designee until the event resolves, or the condition stabilizes to a level acceptable to the investigator, until the event is otherwise explained, or until the participant is lost to follow-up. New or updated information will be recorded in the originally completed eCRF and the investigator will submit any updated SAE information to the sponsor within 24 hours of receipt of the information.

SAFETY REPORTING OVERSIGHT

In accordance with International Council for Harmonisation (ICH) Good Clinical Practice (GCP), the Sponsor or designee will inform investigators of findings that could adversely affect participant safety, impact the conduct of the trial, or alter the IRB's approval/favorable opinion to continue the trial.

The Sponsor has a legal responsibility to notify both the local regulatory authority and other regulatory agencies about the safety of an investigational treatment. The Sponsor will comply with country-specific regulatory requirements relating to safety reporting to the regulatory authority, IRB, and investigators.

An investigator who receives an investigator safety report describing SAEs or other specific safety information (e.g., summary or listing of SAEs) from the Sponsor will file it along with the Investigator's Brochure (IB) and will notify the IRB, if appropriate, according to local requirements.

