5.2 EFFICACY ASSESSMENTS

The following table summarizes the efficacy and safety assessments that will be used for primary, secondary, and exploratory endpoints during the study period.

Assessment	Endpoint Type	Definition
HAM-D	Primary	
 The HAM-D17 is a 17-item clinician-rated measure of depression (Hamilton, 1960). The HAM-D6 is a subset of the HAM-D17 that assesses 6 core items associated with major depression: depressed mood (item 1), feeling of guilt (item 2), difficulty performing work and activities (item 7), motor retardation (item 8), psychic anxiety (item 10), and somatic symptoms (general, i.e., low energy and bodily pain) (item 13) Item 13 is scored 0 to 2 (0 = none/absent to 2 = most severe) and all other items are scored 0 to 4 (0 = none/absent to 4 = most severe). Total score ranges from 0 to 22 and a higher score indicates greater severity of depression. The HAM-D is commonly used for diagnostic purposes in research, and structured clinical interviews such as this are recommended to formally diagnose clinical depression (Norhayati et al., 2015). The HAM-D17 will be administered at baseline via the Structured Interview Guide for the Hamilton Depression Rating Scale (SIGH-D 17-item HAM-D), at Week 4, and Week 8 to derive HAM-D6
EPDS	Secondary	
 A brief self-report questionnaire used as a screening tool to identify patients who are at risk for perinatal depression (Cox et al., 1987; Wisner et al., 1994). The 10-item scale assesses depression criteria (including anhedonia, anxiety, sleep disturbance, and suicidal ideation) in the past seven days. Each item has four ordinal response options, yielding a total score of 0 to 30 where a higher score denotes greater depression (values ≥ 10 denote possible depression). The EPDS is a widely used measure with demonstrated reliability and validity for the assessment of depression (Yawn et al., 2009; Zhong et al., 2014), and is also routinely used in clinical care practice for the assessment of patients with PPD. The EPDS will be administered at baseline, Week 4, and Week 8.

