7. DATA AND SAFETY MONITORING

Data monitoring will be conducted by the research coordinator and site staff (research team) and overseen by project PIs.

During data collection and monitoring, study coordinators will follow an internal safety protocol and alert a study PI of any clinical concerns. A clinical concern is defined here as any negative experience or symptom that occurs during baseline or post randomization sessions that are raised via email/text/phone correspondence directly by the patient, or in key assessment visits to the CIR, whether it is associated with participation in the study.

The PIs in consultation with study site staff will be responsible for monitoring participant safety during the study and will review relevant data/information to determine whether it is appropriate for the participant to continue study participation and whether further action to ensure the safety and wellbeing of the participant is warranted.

Given this study will be conducted among women with PPD, there are clinical concerns that may be anticipated in the target patient population due to the natural course of disease. Anticipated clinical concerns may include suicidal ideation, clinically significant deterioration in depressive symptoms, self-injurious behavior, suicide attempts, and completed suicide. These events will be recorded and will be elevated to AE or SAE status if deemed appropriate by the investigator, and promptly reported to the Sponsor. As part of a Safety Monitoring process, all AEs/SAEs will require DSMB review, and the Sponsor can query any PI-determined AEs/SAEs.

TABLE 3 CLINICAL CONCERN CATEGORIZATIONS

Clinical Concern	Definition
0 - Not a clinical concern:	Qualified research personnel determined that triggering event was not a clinical concern

Sponsor Name: Woebot Health

Protocol Number: WB001-001

1- Mild clinical concern:	Qualified research personnel determined that triggering event doesn't require investigator input and will continue to monitor participant's responses
2- Moderate clinical concern:	Qualified research personnel determined that triggering event requires investigator input. PI/Clinician determined that the research team should continue to monitor participant's responses but that no follow-up was needed.

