9.5 ANALYSIS OF SAFETY

The Safety Analysis Set will be used for the analysis of AE data.

AEs will be coded with MedDRA. All AEs with an onset date on or after the date of first use of the investigational product and before the date of last use of the investigational device will be collected and presented by system organ class and preferred term in frequency tables. Participants with multiple AEs will be counted only once within each preferred term and system organ class. Key participant information for participants with an AE with an outcome of death, participants with SAEs, and participants with an AE leading to withdrawal from the study will be listed.

Sponsor Name: Woebot Health

Protocol Number: WB001-001

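### The single-unifying-diagnosis rule for AE terms has no exception for suicidality, so new suicidal ideation may be reported only as worsening PPD and be missing from the by-arm preferred-term tables.

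*Combined protocol and SAP*

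**What the plan says.** The event-term rule appears twice. In Section 7.2, under AE severity: "If possible, investigators should report event terms that reflect a single, unifying diagnosis rather than individual signs or symptoms". The examples there are influenza and anemia. In Section 7.3, under documenting and reporting: "Whenever possible, a single unifying diagnosis should be reported as the event term, and not the individual signs and symptoms". Both statements are conditional. Neither mentions PPD or suicidality, and neither lists an exception.

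Section 9.5 says how reported terms reach the results. AEs are coded with MedDRA and are to be "collected and presented by system organ class and preferred term in frequency tables". Within those tables, "Participants with multiple AEs will be counted only once within each preferred term and system organ class". No grouping of preferred terms and no event of special interest is defined for suicidality.

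Section 7 treats the same events as separate items: "Anticipated clinical concerns may include suicidal ideation, clinically significant deterioration in depressive symptoms, self-injurious behavior, suicide attempts, and completed suicide". It continues: "These events will be recorded and will be elevated to AE or SAE status if deemed appropriate by the investigator". This passage gives no instruction on the event term to use.

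The synopsis lists the C-SSRS as a safety endpoint beside AEs and SAEs. Section 9.4 promises a descriptive summary of all safety variables by randomized treatment, and a between-group comparison of AEs and SAEs that participants report or that the investigator detects through the C-SSRS.

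**The concern.** A unifying-diagnosis rule is ordinary good practice when the symptoms have little interest apart from the diagnosis. Here the obvious unifying diagnosis is the disease under study, and one of its symptoms is the safety outcome of most interest. The EPDS entry in Section 5.2 places suicidal ideation among the depression criteria, and the benefit/risk section names worsening of PPD as the main risk that could lead to AEs. An investigator applying the rule could enter worsening PPD alone for a woman whose depression deteriorates with new ideation. In the Section 9.5 tables she would then look the same as a woman who deteriorates without ideation.

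The safety aim in the synopsis relies on the C-SSRS, PHQ-9 item 9, EPDS item 10 and HAM-D17 item 3 to help identify AEs and SAEs. What these instruments pick up is suicidality. If the reported term drops that content, an imbalance between arms in ideation could sit inside similar counts of worsening PPD.

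**Working it through.** The documents give no figure on this point, so the main check is to follow one case through the text.

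**Case: a woman on study with worsening PPD and new, non-serious suicidal ideation, who does not withdraw.**

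1. *Detection.* Section 5.3 flags the event through the C-SSRS, an item score or a contact between visits. The C-SSRS is scheduled for baseline, Week 4 and Week 8. At an unscheduled safety contact, or after an item flag, it is given only if judged necessary.
2. *AE status.* Section 7 has the event recorded and leaves elevation to AE or SAE to the investigator.
3. *Event term.* Sections 7.2 and 7.3 prefer one diagnosis over its symptoms. Ideation is a symptom of depression, so worsening PPD alone complies with the rule. Entering ideation as its own term is not forbidden, because the rule is conditional.
4. *AE table.* Section 9.5 tabulates the term that was entered. If that was worsening PPD alone, ideation has no row. Counting each woman once per term is not part of the problem: a woman with two reported terms appears under both.
5. *Listings.* Section 9.5 lists deaths, SAEs and AEs leading to withdrawal. This case is none of these.
6. *C-SSRS output.* Section 9.4 summarises safety variables by arm, so a positive C-SSRS at a visit should appear there. The text gives no categories and no treatment-emergent definition. The comparison of AEs detected through the C-SSRS is a comparison of AEs, so it passes through the same term rule.
7. *DSMB.* Section 7 sends level 4 concerns to the DSMB within 5 working days; ideation without intent can rank lower. Section 7.4 adds quarterly review of all clinical concerns, which does not depend on the AE term.

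**Self-injury and attempts.** These are behaviours or events and not plainly signs or symptoms, so step 3 applies to them less clearly. Level 4 reporting covers them.

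**Homicidal or infanticidal ideation.** The SCID-5-CT assesses this at screening only (Section 5.1, Appendix 3), and the C-SSRS is described as a measure of suicide risk. No scheduled post-baseline instrument covers it.

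**Illustration of the mechanism. All event counts are assumed.** Take 210/2 = 105 women per arm. Suppose 10 women on WB001 worsen with new ideation and 8 without, and 2 women on ED001 worsen with new ideation and 16 without. Each arm then has 18 with worsening. Let f be the share of ideation cases entered only as worsening PPD, equal in both arms. The ideation row shows (1 − f) × 10 against (1 − f) × 2.

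| f | Ideation row, WB001 vs ED001 | Fisher exact p, two-sided |
|---|---|---|
| 0 | 10/105 (9.5%) vs 2/105 (1.9%) | 0.033 |
| 0.5 | 5/105 (4.8%) vs 1/105 (1.0%) | 0.21 |
| 1 | 0/105 vs 0/105 | 1 |

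If worsening PPD is entered for all of these women, its row reads 18 vs 18 at every f. The counts were chosen so that the arms match on worsening. The table shows what can be lost from the preferred-term rows; it does not forecast how much will be.

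**The case against.** The strongest reply is that the rule is generic wording about clean event terms, is conditional, and is illustrated only by non-psychiatric examples. The study-specific text points the other way: Section 7 names ideation, self-injury and attempts apart from deterioration, and Section 5.3 makes a HAM-D17 item 3 score of 2 or more a potential safety event in its own right. A sensible investigator would probably report ideation as ideation. This stands as far as it goes: the rule permits relabelling and does not compel it. But Section 7 settles what is recorded as a concern, not which term is entered once it becomes an AE, so it does not override Sections 7.2 and 7.3.

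A reader might infer more: that suicidality would disappear from the trial's safety results, or that the DSMB would not see it. The documents do not support that. The by-arm C-SSRS summary, the listings and the DSMB's review of clinical concerns all remain. Each AE record must also carry a description of the event (Section 7.3). A reader might equally infer that suicide attempts would be hidden as worsening PPD; the wording does not clearly reach behaviours, and attempts follow the level 4 route.

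Some relevant detail is also out of sight. Text after the C-SSRS description and the escalation scenarios is redacted, and the protocol refers to a DSMB charter and a Protocol Supplement that are not in the material reviewed. A term convention or separate suicidality rows may be set out there.

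**Conclusion.** The point holds in a limited form. As written, Sections 7.2 and 7.3 allow new suicidal ideation to be reported only as worsening PPD, so it may be missing from the by-arm preferred-term tables of Section 9.5. The safeguards elsewhere narrow the gap without closing it. Least well covered are non-serious ideation arising between scheduled C-SSRS assessments in a woman who stays in the study, and homicidal or infanticidal ideation after baseline.

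The size is unknown, because the documents do not allow the frequency of relabelling to be derived. The conclusion rests on two assumptions: that some investigators apply the rule literally to a symptom of PPD, and that no term convention in the redacted or separate documents already prevents it. This is a cheap improvement to a stated rule and not a failure of the safety plan.

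**What to change.** Add one sentence to each of Sections 7.2 and 7.3: when reported as AEs or SAEs, suicidal ideation, suicidal behaviour, self-injury, and homicidal or infanticidal ideation keep their own event term in addition to any unifying diagnosis such as worsening PPD. Repeat this in the eCRF completion instructions. In Section 9.5, show these terms by arm as their own rows beside the C-SSRS summary promised in Section 9.4.

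The cost is a sentence in two places, a completion note and one group of table rows. Some women will contribute two terms instead of one. The change needs no new visits, assessments or data, and it affects only how events are named and tabulated.

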7.4 DATA SAFETY MONITORING BOARD (DSMB)

The Data Safety Monitoring Board is co-responsible for the oversight and safety monitoring of the study. The DSMB advises the Sponsor regarding the continuing safety of the trial participants and those yet to be recruited to the trial, as well as the continuing validity and scientific merit of the trial. The team assembled for the DSMB will have relevant and complementary expertise in psychiatry, obstetrics and gynecology, clinical trial design, digital health, and statistics. This DSMB should include members from academic sites independent of the study sites and should consist of at least one non-study, board-certified psychiatrist and one biostatistician.

Sponsor Name: Woebot Health

Protocol Number: WB001-001

Importantly, none of these individuals will be involved in any other capacity with this study or have any potential conflicts of interest in study-related outcomes.

The DSMB will review and evaluate information relevant to the safety of this study before the implementation of the protocol. Activities of the DSMB will include:

1. Developing the DSMB Charter that will be approved by the Sponsor (including study stopping criteria and final interim analyses being conducted by the independent statistician etc.)
2. Reviewing the study protocol at the start of the study and any proposed amendments related to changes in study design, safety monitoring, or analytic plan
3. Recommending alterations to the study design
4. Approving the study protocol before commencement
5. Performing expedited monitoring of unanticipated serious adverse device effects at the time of their occurrence and providing recommendations accordingly
6. Performing quarterly review of all clinical concerns
7. Performing ongoing quarterly review of study progress
8. Reviewing any data that may reflect differences in safety between treatment groups
9. Determining whether study procedures should be changed, or the study should be halted for reasons related to the safety of study participants
10. Performing quarterly review of the completeness and validity of data to be used for analysis of safety and efficacy.

